## 8.3 Access to Source Data

During the study, the Sponsor/CRO site CRA will make regular site visits to review protocol compliance, conduct source data verification by comparing e-CRF entries and individual patient's medical records, assess drug accountability and management, assess laboratory procedures and ensure that the study is being conducted according to pertinent regulatory and protocol requirements. The review of medical records will be performed in a manner that ensures patient confidentiality is maintained. Remote review of source data can be performed if permitted by the study site.

Source data verification will be required to monitor the progress of the study. Moreover, regulatory authorities in certain countries, IECs/IRBs and/or the Sponsor's Clinical Quality Assurance Group or designee may wish to carry out such source data checks and/or on-site audit inspections. Direct access to source data will be required for these inspections and audits; they will be carried out giving due consideration to data protection and medical confidentiality. The Investigator must assure the

CRO and the Sponsor that they will provide the necessary support at all times. Also U.S. Department of Defense providing funding for the study can access source records as part of study oversight.

## **8.4 Archiving Study Records**

It is the responsibility of the Principal Investigator to ensure all essential trial documentation and source records (e.g., signed Patient Information and Consent Documents, Investigator Site Files, Pharmacy Files, patients' hospital notes, copies of eCRFs etc.) are stored in secure archives for 25 years after the end of the trial. However, these documents should be retained for a longer period if required by applicable legal requirements. The Sponsor's approval is required prior to transfer or destruction of the documents.

## **8.5 Good Clinical Practice**

The procedures set out in this study protocol are designed to ensure that the Sponsor and Investigator abide by the principles of the Good Clinical Practice guidelines of the ICH and the Declaration of Helsinki (Declaration of Helsinki 2013). The study will also be carried out in keeping with local legal requirements.

## **8.6 Informed Consent**

The Investigator at each investigational site is responsible for ensuring that written informed consent for study participation is given by each patient or their legal representative prior to collection of study data and administration of the study drug. Unless the study site is in a country where consent can only be obtained from the patient but can be waived and obtained retrospectively, according to local IEC rules, the Investigator will not undertake any investigation specifically required only for the clinical study until valid consent has been obtained. If consent has not been obtained, a patient cannot be enrolled into the study.

Consent will be sought from the patients themselves, if this is possible. However, it is recognised that some patients may be unable to give written informed consent themselves due to severity of the clinical condition. For these patients, written informed consent will be sought from a PerLR or PrfLR. The PerLR may be a relative, partner or close friend. Any country-specific guidance on who may act as a PerLR will be followed. If the patient is unable to give consent and no PerLR is available then a doctor at the investigational site who is not connected with the conduct of the study may act as a PrfLR (in countries where this process is acceptable). Any country-specific guidance on who may act as a PrfLR will be followed. In some countries, according to IEC rules, consent can only be obtained from the patient. In these countries, if the patient is unable to give consent, their relatives and the patient's own family doctor will be informed about the study. Consent from the patient will be obtained as soon as the patient is able to understand the study and sign the consent form. The appropriate guidances and laws will be followed for each country participating in the study.

If a protocol amendment is required, the ICD may need to be revised to reflect those changes. If the ICD is revised, it must be reviewed and approved by the appropriate IEC/IRB and signed by all patients (or their representatives) subsequently enrolled in the study as well as those currently enrolled in the study where relevant.

### **8.6.1 Consent Procedure**

The person giving consent will be informed about the study by the Investigator or by a member of the research team to whom the Investigator has delegated the consent process. The patient will also be given a copy of the ICD.

To provide all the necessary information, clinical study information and ICDs are quite lengthy. For this study, dependent on country or site specific regulations, an abbreviated initial section of the ICD will provide a short summary of key information, followed by the detailed information for those interested in receiving further information.

The patient, PerLR or PrfLR must be given adequate time to consider their decision about entering the study. However, the requirement to initiate study treatment within 48 hours of admission to hospital meeting inclusion criteria will of necessity be a consideration.

In all cases, the patient, PerLR or PrfLR will be asked to sign two copies of the ICD, which will then be countersigned by the Investigator or the member of the study team to whom obtaining consent has been delegated. One copy of the document will be retained by the person giving consent (patient, PerLR or PrfLR). The second copy will be photocopied. The photocopy will be placed in the patient's medical records, if allowed by hospital's regulations, and the original will be retained in the Investigator Site File. Alternative practical arrangements, including electronic consent processes, might be used due to e.g., COVID-19 restrictions at the hospitals.

A similar procedure will be followed for retrospective patient informed consent, which will be an additional section at the end of the ICD (see [Section 8.6.2](#)).

The terms of the consent and details of the informed consent discussions should be recorded in the subject's medical notes; this should include the date the consent was given and the short name of the study or protocol code.

### **8.6.2 Retrospective Patient Informed Consent**

Patients for whom consent was given by a PerLR or a PrfLR will be informed of their participation in the study by the Investigator or by a member of the research team to whom the Investigator has delegated the consent process. This process will take place once the patient has regained the capacity to understand the details of the study. The timing of this process will thus vary between patients. However, every attempt to obtain retrospective consent must be made when the patient's condition is appropriate. If a patient's condition has precluded the re-consent process occurring by D90 (3 months), then no further attempts will be made to re-consent the patient.

Once informed, patients will be given an adequate amount of time to consider their decision to consent to continued participation in the study and to sign the re-consent section of the ICD.

If the patient does not give retrospective consent then the patient will be informed of the importance to collect the data and that the data collected from the patient to that time point will be entered into the analyses as the withdrawal does not extend to the data already obtained during the time the subject was enrolled. Blood samples already collected up to the time of withdrawal will be analyzed. Genetic samples collected will be analysed per protocol. No further data will be collected; the patient will be considered as withdrawn and the reason for withdrawal will be 'retrospective consent not given'.

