## 4.8 Patient Withdrawal and Replacement

### 4.8.1 Discontinuation Criteria

Subject may withdraw from the entire study, including follow-up, at any time without penalty and for any reason without prejudice to their future medical care; they are not obliged to state their reasons for withdrawing. The decision to withdraw can be made by the subject or their Personal Legal Representative (PerLR) or Professional Legal Representative (PrfLR).

Subjects may be **withdrawn from the study** under the following circumstances:

- Protocol violations including non-compliance with study procedures or subject lost to follow-up
- Subject, PerLR or PrfLR request

The Investigator must ensure that the status page in the e-CRF for the **end of the study** is completed. Necessity for concomitant glucocorticoid treatment during study days D1-D6 may occur (for treating conditions listed in the [Table 1](#) or based on Investigator's judgement for other conditions necessitating **systemic (oral or intravenous)** glucocorticoid treatment) or deterioration of the study subjects condition due to COVID-19 may lead to IMP discontinuation and initiation of open label corticosteroids for COVID-19, neither of these are a condition for withdrawal.

Subject may be required to **withdraw from study drug** after discussion with the Sponsor and/or Investigator for the following reasons:

- Safety issues
- At the discretion of the attending physician if it is considered to be in the subject's best interest

Subjects who discontinue study drug should continue in the study for follow-up to D90. The Investigator must ensure that the status page in the e-CRF is completed and every effort should be made to minimize missing data.

In all cases, the reason(s) for withdrawal, including the primary reason, must be recorded in the e-CRF. If a subject is prematurely withdrawn from the study drug for any reason, the Investigator must make every effort to perform the evaluations described for the follow-up visits. Any on-going AEs should be followed up to resolution or D28 whichever is the sooner. D90 assessment for mortality should be sought to the extent possible. See also [Sections 8.6.2](#) and [8.6.3](#).

If a subject (or their representative) withdraws consent and still agrees to undergo a final examination, this will be documented in the e-CRF and the Investigator's copy of the Informed Consent Document (ICD), which will be countersigned and dated by the subject (or PerLR or PrfLR).

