#### 7.2.1.4 Missing Data Handling

In general, data will not be imputed for the primary efficacy analysis or the safety analysis. For other efficacy analyses, where relevant, imputations will use the last observation carried forward method for patients in the analysis. Additional details will be given in the SAP.

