### **8.6.3 Withdrawal of Consent**

Patients may withdraw or be withdrawn (by the PerLR or PrfLR) from the study at any time, for any reason and such a decision will not affect the ongoing care given to the patient. Data recorded and biospecimen collected up to the point of withdrawal will be included in the study analyses.

If a patient or PerLR/PrfLR requests termination of the administration of study drug during the treatment period, then the administration of study drug will be stopped but the patient will continue in the study and all follow-up assessments will be performed.

If a patient or a PerLR/PrfLR withdraws consent during or after the treatment period then the administration of study drug will be stopped and no further active study assessments will be performed from that point on. However, permission will be sought to access the patient's medical records to obtain data relevant to the study and safety evaluation (e.g., mortality, etc.). If a patient (or their representative) withdraws consent and still agrees to undergo a final examination, this will be documented in the e-CRF and the Investigator's copy of the Informed Consent Document (ICD), which will be countersigned and dated by the subject (or PerLR or PrfLR).

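### Section 8.6.2 stops all data collection when retrospective consent is declined, without the records-permission step of 8.6.3, and is not reconciled with D90 mortality follow-up or death reporting

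*Protocol*

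**What the plan says.** Protocol 8.6.2 covers people who did not consent for themselves: "Patients for whom consent was given by a PerLR or a PrfLR will be informed of their participation in the study". On timing: "This process will take place once the patient has regained the capacity to understand the details of the study". Attempts may continue until D90. If the patient declines, data obtained up to then are kept, because "the withdrawal does not extend to the data already obtained during the time the subject was enrolled". After that, "No further data will be collected; the patient will be considered as withdrawn".

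Protocol 8.6.3 covers withdrawal of consent, by the patient or a representative. Active assessments stop there too, but the section goes on to a request: "no further active study assessments will be performed from that point on. However, permission will be sought to access" the medical records, for study and safety data with mortality as the example.

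Protocol 4.8.1 says "D90 assessment for mortality should be sought to the extent possible" and then refers the reader to both 8.6.2 and 8.6.3. Sections 6.6.1.2 to 6.6.1.5 require all deaths up to D90 to be reported as SAEs. Sections 4.8.1.1 and 6.5 look for vital status from other sources even when a patient is lost to follow-up.

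On analysis, the primary endpoint is the D14 WHO score in the FAS under a treatment-policy strategy (7.2.1.5, 7.5.1). Section 7.2.1.4 says that, in general, "data will not be imputed for the primary efficacy analysis".

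**The concern.** Two things are at stake.

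The first is consistency. Take a patient who declines at D10 and dies at D20. Section 8.6.2 says to collect nothing more. Section 4.8.1 says to seek D90 mortality, and the safety sections say to report the death. Section 8.7 asks for the protocol to be followed exactly, so a site has no way to comply with all of it. The D28 and D90 mortality endpoints and the safety data would then depend on which section the site reads.

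The second is selective loss. Only a patient who has regained capacity can be asked, so only such a patient can decline. Someone who dies by D14 without having been asked keeps a score of 8. Someone who recovers and declines before D14 has no D14 score and, with no imputation, drops out of the primary analysis. By this route, then, missingness depends on something that happens after randomisation and is related to outcome. Much of the loss could be avoided, since the protocol already uses a records-permission step in 8.6.3.

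**Working it through.** **The rules side by side**

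| Situation | Data before the decision | Data after it |
|---|---|---|
| Retrospective consent declined (8.6.2) | kept | none; no request for records access |
| Consent withdrawn (8.6.3) | kept | no active assessments; permission sought for records |
| Lost to follow-up (4.8.1.1, 6.5) | not addressed there | mortality sought from other sources |
| Any death to D90 (6.6.1.2 to 6.6.1.5) | reported as SAE | reported as SAE, with no exception for 8.6.2 |

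**The plan's own figure.** Section 7.4 gives 80% power with 70 evaluable patients per group at an odds ratio of 0.43, two-sided alpha 0.05. Whitehead's proportional-odds formula is n per arm = 6(z_α/2 + z_β)² / [(ln OR)² f], where f = 1 − Σp̄³ and p̄ is the mean category share over the two arms. With f = 1, n = 6 × (1.960 + 0.842)² / 0.844² = 66.1. Exactly 70 per arm needs f = 66.1/70 = 0.944. The planned D14 distribution is not given (the SAP's sample size appendix is not reproduced), so two control distributions were assumed for categories 0 to 8:

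- mid-spread: 5, 20, 25, 12, 15, 8, 5, 3, 7%; f = 0.961, power at 70 per arm 80.7%
- many discharged: 5, 35, 25, 8, 10, 6, 4, 2, 5%; f = 0.910, power 78.5%

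These bracket the stated 80%.

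**Size of the loss.** The assumptions are:

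- 5-30% of patients are entered by a representative
- 10-50% of those decline before D14
- the loss falls only on D14 categories 0-3
- given outcome, refusal does not differ by arm

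Expected loss per arm = 70 × (share in categories 0-3) × (representative share) × (refusal rate). For the mid-spread case at 20% and 25%, the shares in categories 0-3 are 0.62 (control) and 0.792 (IFN). So the loss is 70 × 0.62 × 0.05 = 2.2 and 70 × 0.792 × 0.05 = 2.8.

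A proportional-odds model was then fitted to the remaining expected counts. Power = Φ(|ln OR| √(N f/12) − 1.96), with N = 4/(1/n₁ + 1/n₂) and f recalculated.

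| Distribution | Representative × refusal | Scores lost (control, IFN) | OR | Power |
|---|---|---|---|---|
| Mid-spread | 5% × 10% | 0.5 (0.2, 0.3) | 0.430 | 80.6% |
| Mid-spread | 20% × 25% | 4.9 (2.2, 2.8) | 0.429 | 79.6% |
| Mid-spread | 30% × 50% | 14.8 (6.5, 8.3) | 0.426 | 77.3% |
| Many discharged | 5% × 10% | 0.6 (0.3, 0.3) | 0.430 | 78.4% |
| Many discharged | 20% × 25% | 5.6 (2.6, 3.0) | 0.428 | 77.4% |
| Many discharged | 30% × 50% | 16.7 (7.7, 9.1) | 0.425 | 74.8% |

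With no treatment effect the fitted odds ratio is 1.000 throughout. The largest power loss is 78.5 − 74.8 = 3.7 points. In the worst mid-spread case the observed D14 death share moves from 7.0% to 0.070/(1 − 0.62 × 0.15) = 7.7% in control, and from 3.1% to 3.6% on IFN.

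A second simulation gave representative-entered patients worse outcomes (1.5 on the log-odds scale). It took 10-30% so entered and 20-30% refusal among those at category 4 or lower. It lost 0.8-3.2 of 70 control and 1.0-4.7 of 70 IFN patients. The odds ratio before and after was 0.442/0.439, 0.457/0.453, 0.455/0.449 and 0.463/0.456.

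Neither calculation includes deaths after refusal. The documents give nothing from which to size them.

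**The case against.** A stricter rule for people who never consented themselves may be deliberate, and 8.6.2 already has the site explain why the data matter. That is a fair reading. It does not explain why no permission is asked, and if the strict rule is intended, 4.8.1 and the death-reporting sections still need an exception.

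The conflict with 4.8.1 is narrow. It concerns D90 mortality only and is qualified, and the cross-reference could be read as setting the limits. The sentence there about continuing follow-up to D90 concerns stopping study drug. This stands, but the two sections it points to still differ.

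The D14 loss needs representative entry, return of capacity, time to consider and refusal, all before the D14 assessment. A later refusal leaves the primary score intact. The D28 score is secondary and may be carried forward under 7.2.1.4. The Cox model in 7.5.2 would normally keep follow-up to refusal as censored time. Section 7 leaves the handling of withdrawn patients' data to a blinded review. All of this stands and limits the harm.

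A reader might infer that deaths are always retained while recoveries are lost, so that mortality is systematically overstated. The text does not support this: a death after refusal falls under the same stop on collection. A reader might also infer that 8.6.2 is the only way to lose a D14 score; withdrawal under 8.6.3 and loss to follow-up can do so too.

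**Conclusion.** The inconsistency is real: 8.6.2 lacks the permission step of 8.6.3 and is not reconciled with D90 mortality follow-up or with the reporting of all deaths to D90. Refusals before D14 lose the primary score selectively among patients who regain capacity, and deaths after refusal are lost to the D28/D90 mortality and safety data.

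The numerical effect is probably small. Everything about its size rests on assumed rates and on refusal not depending on arm given outcome. Within the assumed ranges there is no material bias in the odds ratio. It might be tempting to say that the better arm necessarily loses more patients. That follows only from the assumed benefit and recovery-dependent refusal, and at the low end the difference is a fraction of a patient. Section 2.6 describes a mild population on low levels of oxygen, so few are likely to lack capacity and the low end is likelier.

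The SAP reports termination with five patients dosed, and plans listings and descriptive tables without hypothesis tests. No test result is affected. The point concerns the protocol as written.

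**What to change.** In 8.6.2, and in the re-consent section of the informed consent document, replace the outright stop with the 8.6.3 step. A patient who declines is asked for permission to take from medical records the D14 and D28 WHO score (or the facts needed to assign it) and survival and hospital status to D90. Collection ends only if this too is refused. In 4.8.1 and in the death-reporting sections (6.6.1.2 to 6.6.1.5), state what applies when it is refused, so that a site has one instruction to follow.

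The cost is about one sentence in 8.6.2, one line in the consent document, short clarifications in 4.8.1 and section 6.6.1, and ethics approval of the wording. The downside is one more question to a patient who has just declined. Nothing further is taken from records without that patient's agreement.

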### **8.6.3 Withdrawal of Consent**

Patients may withdraw or be withdrawn (by the PerLR or PrfLR) from the study at any time, for any reason and such a decision will not affect the ongoing care given to the patient. Data recorded and biospecimen collected up to the point of withdrawal will be included in the study analyses.

If a patient or PerLR/PrfLR requests termination of the administration of study drug during the treatment period, then the administration of study drug will be stopped but the patient will continue in the study and all follow-up assessments will be performed.

If a patient or a PerLR/PrfLR withdraws consent during or after the treatment period then the administration of study drug will be stopped and no further active study assessments will be performed from that point on. However, permission will be sought to access the patient's medical records to obtain data relevant to the study and safety evaluation (e.g., mortality, etc.). If a patient (or their representative) withdraws consent and still agrees to undergo a final examination, this will be documented in the e-CRF and the Investigator's copy of the Informed Consent Document (ICD), which will be countersigned and dated by the subject (or PerLR or PrfLR).

## **8.7 Protocol Approval and Amendment**

For the study to start, all required documentation must be approved by the IEC/IRB and Competent Authority, in accordance with local legal requirements. The Sponsor must ensure that all ethical and legal requirements have been met before the first patient is enrolled in the study.

This protocol is to be followed exactly. To alter the protocol, substantial amendments must be written, receive approval from the appropriate personnel, and receive IEC/IRB/competent authority approval prior to implementation (if appropriate).

Administrative changes (not affecting the patient benefit/risk ratio) may be made without the need for a formal amendment. All amendments will be distributed to all protocol recipients, with appropriate instructions.

## **8.8 Independent Data Monitoring Committee**

An IDMC will be established for the study. The IDMC and associated parties (CRO, PV, Data management and the Sponsor) will function under the terms of an IDMC Charter. The IDMC will comprise three members, including one independent biostatistician and two senior clinicians with significant experience in clinical management of critically ill patients and who are not involved in the study. The duty of this IDMC is to protect the safety interests of patients and all others who may possibly be exposed to the study drug and to make recommendations to the Sponsor. The IDMC will review ongoing safety data (all SAEs) in an unblinded manner. IDMC meetings are scheduled to take place after the data has been received for the last patient of approximately 20 and 40 subjects and at an interim analysis at 70 subjects who either have completed 14 days in the study following their first dose of study medication or have been withdrawn for any reason (including death). The IDMC will not review efficacy data, other than how it relates to the safety of the therapy. However, the IDMC will review the efficacy data at interim analysis after 70 evaluable subjects, where the sample size re-assessment will be conducted. From each meeting, the IDMC will make a blinded recommendation to the Sponsor regarding the study to continue without change, modify study or enrolment to be placed on hold, or study termination. The sponsor is obligated to inform the study sites, IECs/IRBs and Competent Authorities of the IDMC recommendations according to country specific requirements.

